5. STUDY INTERVENTIONS

5.1 Interventions, Administration, and Duration

Standard Yoga classes are administered to a group of participants. All participants will receive the standard yoga class intervention. Participants will be invited to attend one yoga class per week. Classes may be offered at multiple time slots. Classes will take place via a secure video-based platform such as Zoom; they are planned to be 60 minutes long. Registered yoga teachers will deliver the intervention. Participants from either recruitment site may attend any available class. Potential risks include loss of privacy or breach of confidentiality, increased distress or physical pain due to procedures, ineffective intervention (i.e., lack of improvement in physical pain symptoms), and mild physical injury.

Components of Yoga Intervention are delivered to the participants individually based on randomization assignment. Components include: 1) Personal practice videos featuring study yoga teachers, 2) two 1:1 sessions with a yoga teacher (via a secure video-based platform), 3) Text messages cuing personal practice for the first 3 months, 4) Monetary incentives for class attendance for the first 3 months. Potential risks include loss of privacy or breach of confidentiality, increased distress or physical pain due to procedures, ineffective intervention (i.e., lack of improvement in physical pain symptoms), and mild physical injury.

COVID-related adjustments. We will offer classes and intervention-related meetings via a secure video-based platform on study-provided cell phones in Phase 1 and in Phase 2.

5.2 Handling of Study Interventions

Yoga Intervention

Yoga classes. All participants will receive the manualized hatha yoga program. Participants will be asked to attend one 60-minute class per week for 12 weeks via a secure video-based platform. Each class will consist of: greeting and discussion of personal practice; centering and breath awareness; pranayama (breathing practices); warm up movements; an asana sequence; a seated meditation; and final discussion of personal practice. Classes will acknowledge the validity of participants' pain and gently challenge them to try a new way of coping with it; emphasize breathing in every part of the class; and run the class at a slow pace. Class size will range between 1 and 8 participants.

Yoga Personal practice. Personal practice will be essential for increasing yoga "dosage." When participants first start class, we will give them a yoga mat to take home, a curated list of YouTube videos, and written instructions for personal practices that can be used to manage pain and cope with urges to misuse opioids and other substances. In each class, the yoga instructor will review specific practices and recommend that participants try those practices at home. The practices will always be ones that carry with it minimal risk of injury, and instructors will go over safe practice in class. Participants may continue in the study regardless of whether they practice at home.

Intervention Component 1: Personal practice Videos Featuring Study Yoga Teachers. As part of the standardized yoga intervention, all participants will receive a curated list of YouTube videos for yoga personal practice. However, participants randomized to receive component 1 will also receive study-specific videos of varying lengths featuring study teachers and only yoga practices taught in class. Participants will be randomized to either receive or not receive study-specific videos.

Intervention Component 2: Initial and 1-Month 1:1 Session with Yoga Teacher. Participants randomized to receive this component will receive two 1:1 sessions with the yoga teacher, with one session occurring in the first month of the intervention (ideally right around the time of the first class), and one in the 2nd month of the intervention. (Some flexibility is allowed due to scheduling challenges). Sessions will be via a secure video-based platform. The yoga teacher will address the individual's specific physical concerns and provide individualized advice about a) listening to one's own body; and b) what to do if one is unsure about the physical sensations associated with a specific practice. Participants will be randomized to either receive or not receive 1:1 sessions.

Intervention Component 3: Text messages cuing personal practice. Text messages may be useful to cue participants to engage in yoga personal practice. Immediately post-randomization, for applicable participants, we will ask participants to choose the time of day they would like to receive these messages and whether they prefer to receive them to their study phone, personal phone, or both. Participants will be randomized to either receive or not receive regular text messages cuing personal practice.

Intervention Component 4: Monetary incentives for class attendance. Financial

incentives can increase session attendance for physical activity interventions. Participants randomized to this component will receive \$15 for each yoga class attended. Participants will be randomized to either receive or not receive monetary incentives for class attendance.

Yoga Instructors. The Yoga Alliance is a professional organization which sets standards for yoga teacher training. Teachers will have met criteria to be Registered Yoga Teachers (RYTs) at the Yoga Alliance. Teachers will have study-specific training on research methods, OAT, chronic pain, adverse events, and the yoga manual. They will meet approximately monthly for supervision. Yoga supervisors will also review audio recordings or video recordings of classes to assess instructor adherence.

Yoga instructor Manual Fidelity. All classes will be audio recorded or video recorded. We have developed a fidelity measure that assesses: a) practices used; and b) style, in order to evaluate whether yoga teachers can reliably deliver the manualized program. We will conduct adherence ratings of each teacher's first class, plus an additional random 10% of all other classes on an ongoing basis, and review results with teachers. 1:1 sessions may be recorded as well and reviewed on an as-needed basis.

Yoga Intervention After Initial 12 weeks.

Participants who are in the study follow-up period (i.e., have completed their initial 12 weeks of yoga classes) will be invited to continue to participate in classes if they wish, provided their participation does not increase a given class size over 8. They will not receive any of the other 4 intervention components.

5.3 Concomitant Interventions

5.3.1 Allowed Interventions

Once a participant is enrolled in the study, participants will not be excluded for any concomitant intervention. For example, if a participant begins outside yoga classes or starts a pain management regimen while they are in the study, we will record that information, but not require that they discontinue study interventions. If a participant changes their dose of OAT, type of OAT, or stops taking OAT, we will record that information, but not require that they discontinue study participation.

5.3.2 Required Interventions

None

5.3.3 Prohibited Interventions

None

6. STUDY PROCEDURES

6.1 Schedule of Evaluations

Table 1: Assessment schedule for Phase 1 and Phase 2

Assessment	Screening	Informed Consent Form	Baseline Visit 1	Baseline Visit 2	After initial class	Weekly during M1, M2, M3	M1 visit	M2 visit	M3 visit	M6 visit (Phase 2 only)	Month 9 call (Phase 2 only)	M12 visit (Phase 2 only)	Withdrawal
Inclusion/Exclusion	X		X										
Informed Consent Form		X ⁶											
Enrollment and Randomization				X									
Credibility Expectancy Questionnaire (CEQ)					X								
Weekly Yoga Journal						X				X	X	X	
Injuries due to yoga						X				X	X	X	
Systematic Assessment for Treatment Emergent Events (SAFTEE)										X			
Chart Review ¹			X ²							X ²			X ²
Other Adverse Events			X			X	X	X	X	X			X
SUD, psychiatric, sleep, and pain medications (modified TRAQ)			X							X	X		X
Tampa Scale of Kinesiophobia (TSK)			X				X	X	X				
Self-efficacy for exercise			X				X	X	X				
Logistic Factors							X	X	X				

Assessment	Screening	Informed Consent Form	Baseline Visit 1	Baseline Visit 2	After initial class	Weekly during M1, M2, M3	M1 visit	M2 visit	M3 visit	M6 visit (Phase 2 only)	Month 9 call (Phase 2 only)	M12 visit (Phase 2 only)	Withdrawal
Behavioral Regulation in Exercise Questionnaire (BREQ-2), modified for yoga							X	X	X				
Brief Pain Inventory (BPI) ³			X				X	X	X	X		X	
Numerical Rating Scale (NRS), Pain Severity			X				X	X	X	X		X	
WHO Quality of Life, Brief Version (WHOQOL-BREF)			X						X	X		X	
PROMIS Depression Scale			X						X	X		X	
PROMIS Anxiety Scale			X						X	X		X	
Addiction Severity Index (ASI)			X				X	X	X	X		X	
McHugh Opioid Craving Scale			X				X	X	X	X		X	
Demographics			X										
Review of Medical Comorbidities			X										
Pain Treatment Use			X						X				
Qualitative Exit Interview – Study Procedures (Phase 1: long version; Phase 2: short version)									X			X	
Qualitative Exit Interview-- Intersectional Stigma (Phase 2 only)									X ⁴				
Qualitative Exit Interview-- Study Feedback & Reasons for Withdrawal (Phase 2 only) ⁷													X

Assessment	Screening	Informed Consent Form	Baseline Visit 1	Baseline Visit 2	After initial class	Weekly during M1, M2, M3	M1 visit	M2 visit	M3 visit	M6 visit (Phase 2 only)	Month 9 call (Phase 2 only)	M12 visit (Phase 2 only)	Withdrawal
Payment		\$10	\$10			\$5 for each weekly assmt ⁵	\$20	\$20	\$30 (overall assessment) \$20 (Phase 2 qualitative exit interview, if conducted)	\$30	\$20	\$40	\$20

¹For participants who are not part of the BMC or CODAC system, data typically collected via chart review may be collected by one of the following methods: self-report, pharmacy (with permission of participant), or treatment provider medical records or provider (with permission of participant). For collecting information about medication and dosage, we will have a menu of options for how participants can verify their dose, including methods determined to be secure (e.g., HIPAA-compliant Zoom or Box upload of image). If participants choose to share information through a method that is not secure (e.g., text or email), they will first be consented to the risks of doing so. How data are collected will be clearly marked in the database.

²Chart reviews cover a designated time period (e.g., 3 months before study starts and the time a participant is in the study.) However, staff will typically conduct the chart reviews in batches once a participant completes the study. Therefore, the chart review may not occur immediately at the designated time point, but will cover the designated time period. Note: data collected from chart reviews is limited to treatment with methadone or buprenorphine/naloxone (including dosage, appointments attended, etc.) and does not include any adverse event ascertainment.

³When calculating the BPI- Pain Interference Scale, we will not include the “work” item, as we anticipate that this item does not apply to a large proportion of our sample.

⁴Intersectional stigma interviews will be completed in a subset of participants, including all participants from Phase 1 who agree to complete it, and up to 32 participants in Phase 2. Phase 2 will enroll up to 24 participants who self-report being Black, African American, a related race/ethnicity (e.g., Afrikaner; Black and any other race/ethnicity), and/or Hispanic/Latino/a/x, and up to eight White/Non-Hispanic participants. Efforts will be made to counterbalance Black/African American and Hispanic/Latino/x participants as well as gender within each ethno-racial group where possible. There are no additional inclusion criteria. Using standard study procedures at the 3-month visit, eligible participants will be reminded about the opportunity to participate in an additional exit interview related to their experience of the yoga program and their strengths and resiliency navigating difficult experiences. If participants agree, they will be scheduled for the interview.

⁵This will be paid at the end of each month. Only assessments that are completed within the assessment window (i.e., due date + 6 days) will be compensated.

⁶In order to maximize flexibility for the participant, informed consent may take place at the end of the initial screening, as its own appointment between screening and BL, or at the start of the BL assessment.

⁷The column furthest to the right (“Withdrawal”) may occur at any point between the Baseline Visit 2 and M12, following a participant’s withdrawal from the study intervention, assessments, and/or other study procedures.

6.2 Description of Evaluations

Assessments will be administered by research assistants (RAs) trained in procedures to ensure confidentiality and proper management of research data.

Assessments will be administered via interview (on the phone, via secure video-based platform, or in-person). We will provide participants with a document with response options to look at while they are responding to assessment questions. In cases where, after repeated attempts, we are unable to reach a participant for an assessment via interview, we may email or text (based on participant preference) or an online survey version via REDCap.

We will track the type of interview (on the phone, via secure video-based platform, or in-person) for each assessment.

6.2.1 Screening Evaluation

Consenting Procedure

All phases will have a) agreement from the individual to conduct brief eligibility screening and b) informed consent from the individual at the first visit.

For information about agreement to screening, please see section 4.3 Study Enrollment Procedures.

Screening

For Phases 1 and 2, the screen may be conducted up to 30 days prior to BL.

6.2.2 Baseline – Phase 1 and Phase 2

Consenting Procedure

Informed consent will be obtained prior to or at the baseline appointment.

Please see section 4.3 for more information about the consent procedures.

Documents will be stored in a locked file cabinet, or will be located in REDCap or Box.

Staff at BMC, Butler Hospital, or Cleveland Clinic may conduct informed consent.

Baseline Screening

After informed consent/assent is complete, RAs will confirm eligibility.

If the screening visit occurred > 14 days prior to the baseline visit, they will confirm all eligibility criteria.

If the screening visit occurred \leq 14 days prior to the baseline visit, they will only need to re-confirm the following screening criteria: pain chronicity, pain interference, and pain severity.

To do this, staff will administer the following:

- BPI –Pain Interference

- NRS– Average and worst pain in the past week

If participants meet all eligibility criteria, we will then conduct the remainder of the BL assessments.

For participants who do not meet eligibility criteria, we will inform the individual without stating a specific reason for exclusion. We will provide referrals to the community upon request.

Baseline Assessments – Phases 2

Remaining Baseline assessments include:

- TRAQ
- TSK
- Self-Efficacy for exercise
- WHOQOL-BREF
- PROMIS® Depression Scale
- PROMIS® Anxiety Scale
- ASI
- McHugh Opioid Craving Scale
- Demographics
- Pain Treatment Use

Randomization

Allowable window between BL and randomization is 14 days. Participants are considered enrolled after randomization. The participant is invited to begin the study intervention within 1 week of randomization.

Payment

Payment to participants for completion of the informed consent is \$10, and for completion of the baseline assessment is \$10. The two procedures may be combined in one visit or in separate visits. Participants who attend a visit or phone meeting to complete informed consent will be compensated even if they decline participation in the rest of the study.

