4.2 Exclusion Criteria

All participants meeting any of the exclusion criteria at initial screening or baseline will be excluded from study participation. Details for assessment timing are described below.

Exclusion Criteria – Phase 1 and 2

- 1) Currently taking yoga classes or practicing yoga at home once per week or more often.
- 2) Medical conditions that would make participation in yoga unsafe or not possible, including active malignancy treatment, fracture, recent joint surgery, use of assistive ambulatory devices other than a cane. (In cases where this is unclear, site PI will make final determination based on available evidence.)
- 3) Severe or progressive neurologic deficits. (In cases where this is unclear, site PI will make final determination based on available evidence.)

- 4) Other severe disabling chronic medical and/or psychiatric comorbidities deemed by the site PI on a case-by-case basis to prevent safe or adequate participation in the study (e.g., cognitive impairment that prevents a participant from understanding assessments; history of disruptive behavior in medical settings; severe disabling heart failure or lung disease)
- 5) Surgery requiring overnight hospitalization planned in the next 3 months
- 6) Pregnancy
- 7) No access to a reasonably safe, reliable place to engage in personal yoga practice and a private space to participate in online yoga classes.

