Protections against risk of physical injury. The risk of physical injury will be minimized by: a) excluding participants with contraindicated medical conditions; and b) requiring all instructors to be certified yoga teachers with experience in directing people in how to achieve yoga postures without physical injury; and c) giving all participants a guidebook that explains safer ways to engage in yoga practices. Class content will be designed to accommodate the needs of yoga-naïve students who are not currently physically active. By presenting modifications of all postures, and by using props (e.g., chairs), the risk for injury will be minimal. We will not use postures in this study that are most commonly associated with adverse events, such as headstands, shoulder stands, or handstands.

Potential Benefits

The direct benefits to participants include the possibility of enjoyment of yoga classes and decreased pain. By participating in the clinical research project, participants may benefit from the additional contact with research staff that they will receive. The participant will be contributing to scientific research on optimizing dosage of yoga to the greatest degree possible in an OAT population. Given this level of risk(s) to the patients and the likelihood that some will benefit and the even greater possibility of benefits to the larger population of individuals in OAT through scientific gain, the risk/benefits ratio seems favorable.

Risk-Benefit Ratio.

We believe that most serious risks (e.g., loss of confidentiality, major psychological distress due to study participation, or serious physical injury due to yoga participation) to subjects are very unlikely. We have attempted to minimize these risks (described above). While some risks may be more

likely to occur (e.g., minor, transient psychological distress), these risks are much less serious. Therefore, the potential benefits of the proposed study seem to outweigh the potential risks of this study for the individual participants.

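### When screening was 14 days or less before baseline, no later step requires the exclusion criteria to be asked again, so the last required check can be 35 days old when classes are due to begin

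*Combined protocol and SAP*

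**What the plan says.** Section 4.2 sets the general rule: "All participants meeting any of the exclusion criteria at initial screening or baseline will be excluded from study participation". It leaves the timing of assessment to later text, which is in section 6.2. There, "For Phases 1 and 2, the screen may be conducted up to 30 days prior to BL", and the baseline check depends on how long ago the screen was:

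- Longer gap: "If the screening visit occurred > 14 days prior to the baseline visit, they will confirm all eligibility criteria".
- Gap of 14 days or less: "they will only need to re-confirm the following screening criteria: pain chronicity, pain interference, and pain severity". The tools named for this are the BPI Pain Interference scale and NRS ratings with one-week recall.

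Section 6.2.2 then adds "Allowable window between BL and randomization is 14 days", and invites the participant to start the intervention within a week of randomization.

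Section 4.3 (Enrollment and Randomization) makes randomization depend on completed baseline assessments, inclusion criteria passed, and confirmed interest. It does not mention exclusions. Table 1 marks Inclusion/Exclusion at Screening and at Baseline Visit 1, but not at Baseline Visit 2, where randomization sits. Table 1 also schedules a Review of Medical Comorbidities at Baseline Visit 1. That review is not in the section 6.2.2 list of baseline assessments, and no text makes it part of the eligibility decision.

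Section 7 gives, as its first measure against physical injury, "excluding participants with contraindicated medical conditions".

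**The concern.** Several exclusions describe states that can change within days or weeks: current yoga practice (1), conditions that make yoga unsafe, such as a fracture or recent joint surgery (2), neurologic deficits (3), planned overnight surgery (5) and pregnancy (6). Inclusion criterion 6, availability for a class time, can change as well. On the short route none of these has to be asked about after the screen, which section 4.3 describes as a brief contact of 10 to 20 minutes. The 14-day rule looks only at the interval from screen to baseline. It takes no account of the time that may still pass before randomization and the start of classes.

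At stake is a safety procedure. The exclusions are meant to keep people with contraindications out of the classes, and on this route the information behind them may be more than a month old when classes are due to start. For participants recruited at the Cleveland Clinic, which only screens and consents, the Butler Hospital staff who conduct the baseline would not be required to ask about exclusions at all on this route.

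A smaller gap sits in the same paragraph. Chronicity is to be re-confirmed, but criterion 3a concerns the share of days with pain over three months. As described, neither listed tool counts such days.

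**Working it through.** The plan states no figure for the age of the eligibility information, so there is none to reproduce. It can be built from the windows in sections 6.2.1 and 6.2.2.

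**Inputs**
- Screen to baseline, g: 0 to 30 days; the short route applies when g is 14 or less.
- Baseline to randomization: up to 14 days.
- Randomization to invited start: up to 7 days.

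**Formula.** Age of the last required exclusion check when the participant is due to begin = (g if g ≤ 14, otherwise 0) + 14 + 7. At randomization, leave out the 7.

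| Screen before baseline (g) | At randomization | When due to begin |
|---|---|---|
| 0 days | 0 + 14 = 14 | 0 + 14 + 7 = 21 |
| 7 days | 7 + 14 = 21 | 7 + 14 + 7 = 28 |
| 14 days | 14 + 14 = 28 | 14 + 14 + 7 = 35 |
| 15 to 30 days | 0 + 14 = 14 | 0 + 14 + 7 = 21 |

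The most the shortcut adds is 35 − 21 = 14 days. If exclusions were re-asked at baseline for everyone, the last row would apply to all. The 35 days is the sum of the stated windows and not a hard ceiling, because an invitation to begin within a week does not fix the date of the first class.

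**Expected number affected.** The documents give no rate for new exclusion events, so I assume 5 to 15 per 100 person-years. If all 192 participants use the short route with every window at its maximum, the number attributable to the extra 14 days is:
- Low: 192 × 0.05 × 14/365 = 0.4
- High: 192 × 0.15 × 14/365 = 1.1

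**Is there a later check?** Section 4.3 names inclusion criteria only. Table 1 has no eligibility mark at Baseline Visit 2. In section 6.2.2, eligibility is settled before the remaining baseline assessments are given, so a comorbidity review done with those would come after the decision. Nothing says that its findings reopen it.

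**The case against.** The strongest reply is that the short route is a deliberate choice. Sections 4.1 and 4.2 both defer timing, section 6.2.2 supplies it, and a lighter re-check after a recent screen is ordinary practice. This stands as far as it goes. A reader might infer a flat contradiction between 4.2 and 6.2.2, but the deferral rules that out. What remains is that the baseline half of the 4.2 rule has no required check on this route.

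A second reply is that staff are not told to ignore a contraindication they learn of. Under section 4.2 a condition found at baseline still excludes, and the comorbidity review could reveal one. That is a fair backstop, but it depends on chance disclosure, or on a review that section 6.2.2 omits and does not tie to eligibility. Section 7 also lists trained instructors, a guidebook and modified postures, so the exclusions are not the only safeguard.

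Other stronger readings do not hold:

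- **That the most recently screened people have the longest gap.** Someone screened on the day of baseline has 21 days, the same maximum as under the full re-check. The 35-day case is the person at the 14-day limit.
- **That the event rate applies to all 35 days.** Twenty-one of those days exist under the full re-check too; only 14 belong to the shortcut.
- **That the shortcut explains the limits of the surgery exclusion** ("Surgery requiring overnight hospitalization planned in the next 3 months"). Even with a full re-check at baseline, Month 3 can fall 14 + 84 = 98 days later, against about 91 days covered. That is mostly a separate question, and re-dating the exclusion would alter a criterion.
- **That the primary outcome is threatened.** Section 5.3.1 allows outside yoga after enrolment and section 9.5.1 counts it as dosage. Yoga begun between screening and randomization would be unrelated to component assignment.
- **That chronicity cannot be re-confirmed at all.** The text requires it. The likely explanation is a missing item in the tool list, and the documents do not reproduce the BPI questions.

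**Conclusion.** The point holds as a cheap improvement to a safety procedure. For participants screened 14 days or less before baseline, the plan requires no exclusion check after the screen. With all windows at their maximum, that check is 35 days old when the participant is due to begin and 28 at randomization, against 21 and 14 for those screened 15 to 30 days before baseline.

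The expected count is low, about 0.4 to 1.1 of 192. It rests on the assumed event rate and on everyone using the short route at the limit of every window, so within those assumptions it is an upper figure for what the shortcut adds. Sample size, power and the comparison of components are not affected.

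**What to change.** In section 6.2.2:

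1. Have staff re-ask exclusions 1, 2, 3, 5 and 6, and inclusion 6, at baseline for every participant, however recent the screen. The criteria themselves stay as they are.
2. State that a condition found in the baseline Review of Medical Comorbidities counts for eligibility, and add that review to the section's baseline list so that it matches Table 1.
3. Add the criterion 3a question on days in pain to the re-check tools.

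Then align section 4.2, section 6.2.2, the randomization conditions in section 4.3 (which should name exclusions as well as inclusions) and Table 1.

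For the re-asked criteria this lowers the maximum age from 35 to 21 days when the participant is due to begin, and from 28 to 14 at randomization. The cost is a wording change, a short REDCap checklist, a few minutes at a visit that already takes place, and a few more late screen failures.
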